1.0 Study Synopsis

Objectives:

Primary:

1. To evaluate the safety of primary and boost vaccinations with lethally irradiated allogeneic pancreatic tumor cells transfected with the GM-CSF gene vaccine in the treatment of patients with surgically resected adenocarcinoma of the head, neck, or uncinate of the pancreas

Secondary:

1. To estimate the association of specific *in vivo* parameters of immune response including, but not limited to mesothelin, prostate stem cell antigen (PSCA), and mutated *k-ras*-specific T cell responses, with clinical responses in patients who are receiving semi-annual vaccine boosting with lethally irradiated allogeneic pancreatic tumor cells transfected with the GM-CSF gene.
2. To estimate the efficacy of vaccine boosts in the treatment of patients with adenocarcinoma of the pancreas in terms of overall and recurrence free survival.
3. To use the serum GM-CSF levels as a measure of longevity of an allogeneic vaccine following a semi-annual boosting with lethally irradiated allogeneic pancreatic tumor cells transfected with the GM-CSF gene.
4. To determine the psychosocial and symptom profiles of patients with pancreatic cancer treated with an irradiated allogeneic GM-CSF secreting vaccine, and to explore changes over time. The psychosocial profile will include information about, but is not limited to demographics, quality of life, hope, trust, social support, decision control and advanced directives. The symptom profile will include but is not limited to pain, anorexia, fatigue, and mood state.

Study population:

In order to be considered for this study, patients need to meet following major criteria for inclusion: History of surgically resected pathologic stage 1 (no direct tumor extension beyond pancreas and no regional lymph node metastases), 2 (direct extension of tumor beyond pancreas), and/or 3 (regional lymph node metastases) adenocarcinoma of the head, neck, tail, or uncinate of the pancreas.

Have no radiographic evidence of pancreatic cancer disease recurrence.

Have not received any anti-cancer therapy in the past 28 days.

Study Design:

Eligible subjects will receive by intradermal administration the pancreatic tumor vaccine consisting of two irradiated, allogeneic pancreatic tumor cell lines transfected with the granulocyte macrophage-colony stimulating factor (GM-CSF) gene. There will be two cohorts of research participants: those who have previously received the pancreatic cancer vaccine (up to 17) and those

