4.0 Statistical Considerations

4.1 Sample Size

The primary statistical endpoint of this study is to evaluate the safety and feasibility of vaccine boosting with lethally irradiated allogeneic pancreatic tumor cells transfected with the GM-CSF gene. Among patients who have previously been treated with the vaccine, the cohort is limited to those who continue to have no disease recurrence for at least 1 year after treatment. Currently, there are three potentially eligible patients from the original phase I study, and 14 from the phase II study. A total of up to 17 previously treated patients will be eligible to continue to receive vaccine treatment in the form of semi-annual boosts. The second cohort of vaccine naïve patients who have been recurrence free for at least 28 days following adjuvant therapy will be given three priming vaccines each a month apart, followed by semi-annual vaccine boosts in order to determine the feasibility of administering the vaccination to vaccine naïve patients and to obtain initial estimates of the efficacy of such treatment with respect to prolonging disease-free status. As of Amendment #9, participants will be switched to annual vaccinations. We will base our determination of feasibility by estimating the proportion of patients with a dose limiting toxicity (DLT) within 28 days of the first vaccine treatment. Between 20 and 45 vaccine naïve patients will be included. An initial group of 20 patients will be recruited and an interim analysis will be performed in order to guard against excessive toxicities relating to treatment. No DLTs have been observed in either the phase I or II studies. If there is significant evidence that more than 10% of the vaccine naïve patients have dose limiting toxicities within 28 days of the first vaccination, then the trial will be halted. If 6 out of 20 of the initial patients have DLTs, the lower bound of the exact 95% confidence interval for the proportion of patients with a DLT is 11.89%. Therefore, we will halt the trial due to excessive toxicity at the interim analysis if 6 or more patients have a DLT within the first 28 days of their first vaccine. Otherwise, an additional 20 vaccine naïve patients will be accrued. If 20 patients are accrued, the maximum width of the 95% confidence interval estimate of the proportion of patients with a DLT is 0.438. If the full cohort of 40 patients is accrued, then the maximum width of the 95% confidence interval is 0.309.

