The sample size was expanded to include a cohort of up to 45 vaccine-naïve research participants and 17 previously vaccinated research participants for a total sample up to 62 research participants.

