4.2 Analysis of Primary Endpoint: Safety and toxicity measurements

The primary endpoint of this study is safety as measured by local and systemic toxicity. These toxicities will be characterized according to the National Cancer Institute Common Terminology Criteria for Adverse Events, Version 3.0, and can be accessed and downloaded via the website: <http://ctep.cancer.gov/reporting>. Dermatologic toxicity measurements of the vaccine sites will be performed. For each patient cohort (vaccine naïve and vaccine treated), we will tabulate the number, type and degree of toxicities for each round of vaccination. In addition, we will estimate the proportion of individuals who have a DLT within the first 28 days of vaccination for each round with an exact 95% confidence interval.

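### The only numerical trial-level halting boundary is 6 DLTs in the first 20 vaccine-naive patients after their first vaccine; no later look is set, and later primes, boosts and the previously vaccinated cohort have no numerical trigger

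*Combined protocol and SAP*

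**What the plan says.** The primary objective in the Study Synopsis (1.0) is "To evaluate the safety of primary and boost vaccinations". Section 4.1 likewise names the safety and feasibility of boosting as the primary statistical endpoint.

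Section 4.1 gives the halting criterion as a principle: "If there is significant evidence that more than 10% of the vaccine naïve patients have dose limiting toxicities within 28 days of the first vaccination", the trial stops. It applies the principle once: "An initial group of 20 patients will be recruited and an interim analysis will be performed in order to guard against excessive toxicities". The boundary is 6 of 20, justified by an exact 95% lower limit of 11.89%: "Therefore, we will halt the trial due to excessive toxicity at the interim analysis if 6 or more patients have a DLT" in the 28 days after the first vaccine. If it is not reached, "Otherwise, an additional 20 vaccine naïve patients will be accrued", and no second boundary is given. The end of 4.1 then reads "The sample size was expanded to include a cohort of up to 45" naive participants, plus 17 previously vaccinated, again without a further look.

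For later rounds, section 4.2 says "we will estimate the proportion of individuals who have a DLT within the first 28 days of vaccination for each round", with an exact 95% interval, separately by cohort. No threshold or consequence is attached.

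Other safeguards exist without a numerical trigger: removal of individual participants (3.4.3, 3.4.6), reporting of serious adverse events to the IND sponsor and IRB (6.1), and oversight by the Data and Safety Monitoring Committee (7.0).

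**The concern.** The boundary covers a narrow part of the exposure being studied. It counts events in naive patients only, after the first vaccine only, and is evaluated once. Outside it lie:

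- naive patients 21 onward: half of a cohort of 40, and 25 of 45 (56%) at the maximum;
- priming vaccines 2 and 3;
- every boost in both cohorts;
- the whole previously vaccinated cohort, whose first vaccine on study is already a boost (3.4.1.1).

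A DLT after a boost cannot count toward the rule, yet boost safety is what section 4.1 says the trial is to evaluate. Prior experience is also thinnest there. Participants in the earlier phase II study received at most five vaccinations (2.8.1), while boosting here continues until eligibility ends, the participant withdraws or supply runs out. An excess of DLTs in those rounds would be estimated and reported, but nothing in the plan says at what count anyone must act.

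**Working it through.** **Inputs.** From 4.1: threshold 10%, look at n=20, boundary 6, exact two-sided 95% interval, accrual to 40 and then up to 45, previously vaccinated cohort up to 17. The documents give no expected DLT rate, so true rates *p* of 10% to 30% are assumptions shown as a range.

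**1. Reproduce the plan's figure.** The Clopper-Pearson lower limit is L(x, n) = the 2.5% quantile of Beta(x, n−x+1).

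- L(6, 20) = 11.89%, as stated. L(5, 20) = 8.66%, so 6 is the smallest count meeting the criterion. The arithmetic is sound; the gap is in scope.

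**2. Carry the same criterion to other sizes.** This is the smallest x with L(x, n) above 10%.

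- n=40: 9 (10.84%; 8 gives 9.05%).
- n=45: 10 (11.20%; 9 gives 9.58%).
- n=17: 5 (10.31%; 4 gives 6.81%).

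**3. Chance that the single look halts.** P = 1 − Σ(k=0 to 5) C(20,k) p^k (1−p)^(20−k). At p=20% this is 1 − 0.804 = 0.196.

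**4. Chance of halting with looks at 20, 40 and 45.** Keep the paths with at most 5 events at 20, add Binomial(20, p), and stop at 9 or more. Keep the paths with at most 8 at 40, add Binomial(5, p), and stop at 10 or more.

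| True rate | Now: 6/20 only | Passes now | 6/20, then 9/40 | then 10/45 |
|---|---|---|---|---|
| 10% | 1.1% | 98.9% | 2.2% | 2.5% |
| 20% | 19.6% | 80.4% | 43.3% | 47.9% |
| 25% | 38.3% | 61.7% | 71.9% | 76.6% |
| 30% | 58.4% | 41.6% | 89.7% | 92.6% |

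**5. Acting at the sixth DLT.** Six or more events among the first 20 is the same event whether it is noticed when the sixth occurs or at n=20, so the halting probability is unchanged. With N the patient in whom the sixth DLT occurs, P(N=n) = C(n−1,5) p^6 (1−p)^(n−6). Given N ≤ 20, the mean of N is 16.6, 16.1 and 15.4 at p = 20%, 25% and 30%. The average saving among halting trials is therefore 20 minus these, or 3.4, 3.9 and 4.6 enrolments. These are upper figures, because they treat each 28-day outcome as known before the next enrolment.

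**6. Why fixed looks.** Testing the exact limit after every patient up to 45 would raise the false-halt chance at a true 10% to 7.1%, against 2.5% for looks at 20, 40 and 45.

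**7. Later rounds.** With 17 vaccinated and a trigger at 5, the chance of triggering in one round is 2.2%, 24.2% and 61.1% at true rates of 10%, 20% and 30%. By construction the false-trigger chance at 10% cannot exceed 2.5% in any one round. It accumulates: five independent rounds of 17 give 1 − (1 − 0.0221)^5 = 10.6%.

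**The case against.** The strongest defence is that a single early look, aimed at patients never exposed before, suits a product with a clean record. Section 4.1 reports no DLTs in phase I or II. If the phase II experience is taken as 0 of 60, the exact 95% upper limit is 1 − 0.025^(1/60) = 6.0%. At a true 5%, the present rule and the extended looks both halt less than 0.05% of the time. This stands as a reason to expect the boundary not to be needed. It does not explain why a criterion the plan chose to state stops at n=20, and it says less about exposure beyond five vaccinations.

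Three stronger readings are tempting, and the documents do not support them:

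- *Nothing at all protects later patients.* The 10% sentence is not itself tied to n=20 and may be read as continuing for later naive patients' first vaccine. Individual off-study rules, serious adverse event reporting and committee oversight apply in every round. What is absent is a later look, a count and, beyond the first vaccine, any numerical trigger.
- *The DLT rate is never examined after the interim.* Section 4.2 commits to the very interval the criterion needs, by round and cohort. Timing and consequence are missing, not the estimate.
- *A rate three times the limit would probably slip through.* At 30% the single look halts with probability 58%. Passing is the likelier outcome at 20% and 25%, not at 30%.

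**Conclusion.** The concern holds as a gap in scope. There is one trial-level numerical boundary, correctly calculated, for the first vaccine in the first 20 naive patients. The wider principle in 4.1 has no look or boundary after that, and neither principle nor boundary reaches later primes, boosts or the previously vaccinated cohort. For the first vaccine, carrying the plan's criterion to 40 and 45 raises the chance of halting from 20% to 48% at a true 20%, from 38% to 77% at 25%, and from 58% to 93% at 30%. At a true 10% it goes from 1.1% to 2.5%.

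The probabilities assume independent outcomes with a constant DLT rate, and the extended figures assume accrual to 45. The rates of 20% to 30% are scenarios, not expectations from the trial's data. The change should be made because boost safety is part of the primary objective. It does not imply that harm is expected, or that participants lack individual safeguards.

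**What to change.** Amend section 4.1, keeping the plan's 10% threshold and exact 95% criterion:

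- **(a)** Apply the existing boundary when the sixth DLT among the first 20 naive patients occurs, without waiting for n=20.
- **(b)** For the first vaccine, add looks at 40 naive patients (9 or more) and 45 (10 or more). State that no other looks are made, so that the false-halt chance at a true 10% stays at 2.5%.
- **(c)** For each later priming and boost round in each cohort, compute the lower limit on the number actually vaccinated in that round, since participants leave and the denominators shrink (for example 5 of 17 if all 17 are vaccinated). If it exceeds 10%, refer the round to the monitoring committee for review. This is a trigger for review, not an automatic halt.

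Add to section 4.2 that the per-round intervals are produced in time for (c).

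The cost is wording and a calculation on data that 4.2 already requires. The statistical price is the extra 1.4 percentage points of false halting in (b), plus roughly 2% per round in (c) at a true 10% rate, growing with the number of boost rounds. The amendment should state that cumulative cost.

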2.7.1 Summary of Results

This study was the first clinical trial to test the hypothesis that allogeneic GM-CSF secreting pancreatic tumor cell lines can prime a systemic immune response in subjects with resected pancreatic adenocarcinoma. Fourteen subjects with stage 2 or 3 disease received an initial vaccination 8 weeks following resection. This was a dose escalation study in which 3 subjects each received 1×10^7 , 5×10^7 , and 1×10^8 vaccine cells. An additional 5 subjects received 5×10^8 vaccine cells. Study subjects were jointly enrolled in an adjuvant chemoradiation protocol for 6 months. Following the completion of adjuvant chemoradiation, subjects were re-assessed and those who were still in remission were treated with 3 additional vaccinations given one month apart at the same original dose that they received for the first vaccination. Toxicities were limited to grade I/II local reactions at the vaccine site, and self-limited systemic rashes, including one documented case of Grover's syndrome (Davis, Dineen, Landa et al., 1999). Systemic GM-CSF levels were evaluated as an indirect measure of the longevity of vaccine cells at the immunizing site. As was observed in pre-clinical studies, GM-CSF levels peaked at 48 hours following vaccination. In addition, serum GM-CSF levels could be detected for up to 96 hours following vaccination. These data, together with data from pre-clinical models, would suggest that detectable serum GM-CSF levels may serve as a bio-marker of immune response. The vaccine sites were also evaluated as a measure of the local immune reaction to the vaccine. Eleven of 14 subjects demonstrated a similar local inflammatory response to what has been observed in pre-clinical models and autologous GM-CSF vaccine clinical trials. Post-vaccination DTH responses to autologous tumor cells have been used in previously reported vaccine studies as a surrogate to identify and characterize specific immune responses that are associated with vaccination. In the pancreatic cancer vaccine trial, post-vaccination DTH responses to autologous tumor cells were observed in 1 of 3 subjects receiving 1×10^8 and in 2 of 5 subjects receiving 5×10^8 vaccine cells. Three long-term survivors of the initial phase I study are currently participants in the long-term follow-up study (IRB application number NA_00036444, J0248), remain disease-free and have expressed an interest in receiving additional vaccinations. No additional long-term toxicities have been uncovered in this cohort.

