2.8.1 Preliminary Data

Sixty research participants received at least one and a maximum of five vaccinations of two pancreatic cancer cell lines each delivering 2.5×10^8 cells intradermally distributed among three lymph node regions in the Johns Hopkins study, IRB # 00-01-13-02 (SKCCC J9988) entitled, A safety and efficacy trial of lethally irradiated allogeneic pancreatic tumor cells transfected with the GM-CSF gene in combination with adjuvant chemoradiotherapy for the treatment of adenocarcinoma of the pancreas. See Table 2 for the demographic details. Vaccine one was administered 8-10 weeks following surgical resection. Patients were subsequently treated with 5-fluoruracil (5-FU) continuous infusion based chemotherapy integrated with radiotherapy. Research participants who remained disease-free one month after completing the chemoradiotherapy received the vaccines two through four one month apart. A fifth and final vaccine was administered six months after the fourth vaccine.

Table 2. Research Participants' Demographic Data

Characteristic	N=60
Male	37
Female	23
Median age	56.7
Age range	41-83
Node +	52
Margin +	18
Node + and Margin +	18

Enrollment was completed in January of 2005. At an early analysis, 56 patients were evaluable at one year and 36 patients were evaluable at two years. The one and two year survival rates are 88% and 76%, respectively. This data compares very favorably with the available published data.

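### The 10% DLT halt criterion has a scheduled look and a count only at n=20; adding counts at 30, 40 and 45 would be a cheap, optional safeguard for the later vaccine-naive patients

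*Combined protocol and SAP*

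**What the plan says.** All of the rule is in section 4.1 of the combined protocol and SAP.

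- **Criterion.** If there is significant evidence that over 10% of the vaccine-naive "patients have dose limiting toxicities within 28 days of the first vaccination, then the trial will be halted".
- **Look.** "An initial group of 20 patients will be recruited and an interim analysis will be performed".
- **Count.** Six DLTs in 20 give an exact 95% lower bound of 11.89%, so "we will halt the trial due to excessive toxicity at the interim analysis if 6 or more patients have a DLT" within 28 days of the first vaccine.
- **Afterwards.** If the rule is not met, 20 more vaccine-naive patients follow. For n=40 the section gives only a confidence-interval width. A closing paragraph then says: "The sample size was expanded to include a cohort of up to 45" vaccine-naive participants. It does not return to the halt rule.
- **Prior record.** "No DLTs have been observed in either the phase I or II studies".

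Section 4.2 plans an estimate for every vaccination round, with an exact 95% interval: "we will estimate the proportion of individuals who have a DLT within the first 28 days of vaccination for each round". It attaches no action to the result. Sections 3.4.3 and 3.4.6 take an individual patient off study for unacceptable or serious vaccine-related events. Section 6.1 sends serious events to the IRB, and section 7.0 has reportable events reviewed by the DSMC chair or a designee. None of these gives a DLT count for the cohort.

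**The concern.** Safety is the primary endpoint, and the plan itself treats a DLT rate above 10% as grounds to halt. Yet up to 25 of 45 vaccine-naive patients (56%) enrol after the one point at which that criterion is scheduled to be checked.

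The 10% sentence can be read in two ways. If it is general, the action exists for later patients, but nobody is told when to check or which count triggers it. If it only explains the n=20 look, later patients have no numeric rule. Under either reading, 9 DLTs in 40 would meet the plan's evidence standard with no check scheduled to notice it.

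What is at stake is whether a decision is reached if toxicity proves unexpectedly high. Later doses might also be spared, since two priming doses and then boosts follow the first vaccine.

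**Working it through.** **Inputs from the plan (4.1).** Limit 10%; standard: lower bound of the exact two-sided 95% interval above 10%; look at n=20 with count 6; vaccine-naive maximum 45.

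**Step 1: reproduce the plan's figure.** The exact (Clopper-Pearson) lower bound for x events in n is the 0.025 quantile of Beta(x, n−x+1). For 6/20 this is 11.89%, as stated. For 5/20 it is 8.66%, so 6 is the smallest qualifying count.

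**Step 2: extend the same standard.**

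| n | Smallest qualifying count | Lower bound | Bound for one fewer |
|---|---|---|---|
| 20 | 6 | 11.89% | 8.66% |
| 30 | 8 | 12.28% | 9.93% |
| 40 | 9 | 10.84% | 9.05% |
| 45 | 10 | 11.20% | 9.58% |

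The rows after n=20 extend the plan's rule; they are not figures from the plan.

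**Step 3: halting probabilities.** At n=20 the probability is Σ C(20,x) pˣ(1−p)²⁰⁻ˣ over x = 6 to 20. At n=30 it is Σ over x = 0 to 5 of P(X₂₀ = x) × P(Bin(10,p) ≥ 8−x). The looks at 40 and 45 continue this recursion over paths not yet halted. The true rates p are assumptions.

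| True DLT rate | At 20 (plan) | First at 30 | First at 40 | First at 45 | Total 20/30/40/45 | Total 20/40/45 |
|---|---|---|---|---|---|---|
| 10% | 1.1% | 0.4% | 0.8% | 0.2% | 2.6% | 2.5% |
| 15% | 6.7% | 3.0% | 6.4% | 1.9% | 18.1% | 17.7% |
| 20% | 19.6% | 9.0% | 15.4% | 4.4% | 48.4% | 47.9% |
| 25% | 38.3% | 15.0% | 19.0% | 4.6% | 76.9% | 76.6% |
| 30% | 58.4% | 16.8% | 14.8% | 2.7% | 92.7% | 92.6% |

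Totals come from unrounded values. The plan's single look therefore misses true rates of 20% and 30% with probability 100 − 19.6 = 80.4% and 100 − 58.4 = 41.6%.

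**Step 4: how likely is such an excess?** Section 2.7.1 reports the phase I patients at the current dose ("An additional 5 subjects received" 5×10⁸ cells), and section 2.8.1 the phase II patients: "Sixty research participants received at least one and a maximum of five vaccinations of two pancreatic cancer cell lines", at the same total dose. With no DLTs this is 0/65, with exact 95% upper bound 1 − 0.025^(1/65) = 5.5%, if all 65 were assessed on comparable criteria. At a true rate of 5.5%, halting is 0.06% with the plan's look and 0.08% with all four.

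**Step 5: enrolments saved (cap 45).** If L patients enrol while each look is pending, the expected saving is (15−L) × P(halt at 30) + max(0, 5−L) × P(halt at 40). A halt at 45 saves none.

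| True rate | L=0 (accrual paused) | L=5 | L=10 |
|---|---|---|---|
| 20% | 2.1 | 0.9 | 0.5 |
| 25% | 3.2 | 1.5 | 0.8 |
| 30% | 3.3 | 1.7 | 0.8 |

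Accrual speed is not in the documents, so L is a range.

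**The case against.** The strongest reply is that this is a legitimate design: one early safety look in a product with a clean record, then estimation. The prior data support it. If the true rate were 20%, 65 patients without a DLT would have probability 0.8⁶⁵, about 5 in 10 million; at 10% it would be 0.9⁶⁵, about 0.1%. The gain appears only at rates that the record makes improbable. This stands, and it is why the point is optional.

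The reply also notes that the 10% sentence is not confined to n=20 and that section 4.2 already produces the needed interval. That stands too: on the general reading, only the timing and the worked counts are missing.

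On efficiency, the n=30 look adds at most about 0.5 percentage points to a 20/40/45 scheme. One added look at 45 alone reaches 44.4%, 74.0% and 91.5% at true rates of 20%, 25% and 30%. The n=30 look earns its place only by allowing an earlier halt. The saving in doses is also limited, because the day-28 assessment coincides with priming dose 2 (3.4.1.2), which may be given before the count is complete.

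A reader might infer that patients 21 to 45 are unprotected, or that the trial cannot be halted after n=20. The documents do not support this. The criterion can be read as continuing, individual discontinuation, IRB reporting and DSMC review run throughout, and the monitoring plan cited in section 7.0 is not among the documents, so its provisions are unknown.

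**Conclusion.** The point holds as a cheap improvement. Section 4.1 states a halt criterion for the vaccine-naive cohort but schedules its use once, and up to 25 of 45 patients enrol after that. Further counts on the same standard would raise the chance of a halt from 19.6% to 48.4% at a true DLT rate of 20%, and from 58.4% to 92.7% at 30%.

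The benefit is a scheduled decision, with some later doses possibly spared. Few enrolments are saved: about 2 to 3 with an accrual pause at true rates of 20% to 30%, and fewer without one. A reader might take the 80% miss rate as evidence that the plan is unsafe; it is conditional on a 20% DLT rate, which the prior record makes unlikely.

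The figures assume independent patients with a common DLT rate and accrual to 45 unless halted. The 5.5% bound also assumes comparable DLT assessment in the earlier studies. The documents do not say how far vaccine-naive accrual has gone; if it is complete, the earlier looks no longer matter.

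**What to change.** In section 4.1, after the statement that 20 more vaccine-naive patients will follow, add:

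> The same criterion (lower bound of the exact 95% CI above 10%) will be applied to the cumulative vaccine-naive count when the 30th and 40th vaccine-naive patients, and the last patient if accrual reaches 45, complete 28 days after the first vaccine; the trial will be halted at 8 or more of 30, 9 or more of 40, or 10 or more of 45.

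This keeps the 10% limit, the interval method, the 6/20 look and the plan's own action of halting the trial. The team should state whether accrual pauses while a count is completed, and should report the halting probabilities. Dropping the n=30 look gives a simpler scheme that is nearly as sensitive.

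**Cost.** One sentence and up to three counts of DLTs already recorded for the primary endpoint, with no added patients, visits or tests. The downside is a false-halt probability of 2.6% instead of 1.1% at a true rate of exactly 10%, and about 0.08% instead of 0.06% at 5.5%. If accrual is paused, each look may add a delay of up to about 28 days.

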
who are vaccine naïve (30-45). For those patients who have received the vaccine, the boosts will be offered as a continuation of care. For those patients who are vaccine naïve, the feasibility of investigating the use of vaccine priming and boosting to prolong disease free status will be tested. Up to 100 patients may be consented to obtain the targeted accrual goal.

For research participants who have previously received the pancreatic cancer vaccine, the first vaccine boost will be given at least six months after the anniversary date of their last vaccination (+/- 30 days). Since the last vaccination date from the parent vaccine study for some subjects has occurred more than one year ago, they may establish a new semi-annual dates for vaccine boosting. As of Amendment #9, participants will be switched to annual vaccinations. One of the semi-annual or annual vaccine boost dates will be the same as their annual long term-follow-up visit date.

For research participants who are vaccine naïve, their first vaccine will be given at least 28 days after their last anti-cancer therapy. The vaccine naïve research participant will receive priming vaccinations once every month for a total of three vaccines, and then will receive the vaccine boosting on a semi-annual basis. As of Amendment #9, participants will be switched to annual vaccinations.

The vaccine will be administered once every six months (+/- 30 days) after the previous vaccine until the subject no longer meets the eligibility criteria, no longer wishes to participate in the study, or the vaccine supply is exhausted. In the event that the eligibility criteria are not met, the subject may be re-evaluated if the Principal Investigator anticipates that the research participant may meet the eligibility criteria later. As of Amendment #9, participants will be switched to annual vaccinations (+/- 30 days). If eligibility is later established, a new anniversary date for vaccine boosting and long-term follow-up will also be set as the date of the most recent vaccination.

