3.2 Study Population

Patients with surgically resected pathologic stage 1 (no direct tumor extension beyond pancreas and no regional lymph node metastases), 2 (direct extension of tumor beyond pancreas), and/or 3 (regional lymph node metastases) adenocarcinoma of the head, neck, tail, or uncinate of the pancreas and who have no radiographic evidence of pancreatic cancer disease recurrence may be eligible to participate in this study.

There will be two cohorts of research participants: those who have previously received the pancreatic cancer vaccine (no more than 17) and those who are vaccine naïve (30-45). At the time of the initial application of this study there appeared to be 18 research participants of previous pancreatic cancer vaccine studies who may have been eligible for this study. This includes three research participants from the Phase I study and 1 research participants who have completed the protocol-specified vaccines in the Phase II study. Also in this study we estimate enrolling between 30 and 45 research participants who are pancreatic cancer vaccine naïve. Both cohorts of research participants will need to be off all anti-cancer therapy for at least 28 days. It is estimated that we may need to consent up to 100 patients to obtain the targeted accrual goal.

For research participants who have previously received the pancreatic cancer vaccine, the first vaccine boost will be given at least six months after the anniversary date of the off-study visit (+/- 30 days). Since the off-study date from the parent vaccine study may have occurred more than one year ago, new semi-annual dates for vaccine boosting may be established. For research participants who are vaccine naïve, their first vaccine will be given at least 28 days after their last adjuvant anti-cancer therapy.

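### The vaccine-naive cohort size is inconsistent: the accrual rule in 4.1 can end only at 20 or 40, while other text gives 30-45, 20-45 and up to 45, and precision is not stated for the expanded size.

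*Combined protocol and SAP*

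**What the plan says.** Three sections of the combined protocol and SAP give a size for the vaccine-naive cohort.

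- **1.0 Study Synopsis** gives a range of 30 to 45.
- **3.2 Study Population** gives the same range, and repeats it as a forecast: "we estimate enrolling between 30 and 45 research participants who are pancreatic cancer vaccine naïve".
- **4.1 Sample Size** opens with a different range: "Between 20 and 45 vaccine naïve patients will be included". It then sets out a two-stage path. First, "An initial group of 20 patients will be recruited and an interim analysis will be performed". The trial halts if 6 or more of these patients have a DLT within 28 days of the first vaccine. If not, "Otherwise, an additional 20 vaccine naïve patients will be accrued". Precision is given for 20 patients (maximum 95% interval width 0.438) and for the completed path: "If the full cohort of 40 patients is accrued, then the maximum width of the 95% confidence interval is 0.309".
- **The last sentence of 4.1** then states: "The sample size was expanded to include a cohort of up to 45 vaccine-naïve research participants". With 17 previously vaccinated patients, it puts the total at up to 62.

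Section 4.2 plans to report the proportion with a DLT, by cohort and vaccination round, with an exact 95% confidence interval.

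**The concern.** The numbers cannot all describe one accrual plan. The lower end is 30 in two sections and 20 in a third. The completed cohort is 40 in the accrual step and up to 45 in the expansion sentence. The expansion changed the ceiling, but not the step that says how many patients follow a passed interim, and not the width that justifies the size.

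Section 4.1 bases feasibility on the estimated proportion of patients with a DLT, and 4.2 makes that proportion part of the primary safety analysis. The naive-cohort size is its denominator and sets its precision. Someone running the trial from 4.1 would close accrual at 40. Someone working from 1.0 or 3.2 could close it anywhere from 30 to 45. The stated precision would match at most one of those outcomes.

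**Working it through.** **1. Follow the accrual rule.** First stage: 20. Halted: final size 20. Not halted: 20 + 20 = 40. There is no other branch, so 30 and 45 are not reachable. With up to 17 previously vaccinated patients, the path totals at most 40 + 17 = 57. The expansion sentence gives 45 + 17 = 62.

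**2. Reproduce the plan's figures.**

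- Lower bound for 6 of 20, two-sided exact (Clopper-Pearson), the 0.025 quantile of Beta(6, 15): 0.1189. This matches the stated 11.89%, so the plan's exact interval is two-sided.
- Maximum width at 20, Wald formula 2 × 1.96 × √(0.25/n): 2 × 1.96 × √(0.25/20) = 0.4383. This matches 0.438.
- Maximum width at 40, same formula: 2 × 1.96 × √(0.25/40) = 0.3099. This matches the stated 0.309 if truncated; it rounds to 0.310.

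The halting bound is therefore exact, while the two widths are Wald values.

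**3. Widths by the method of the planned analysis.** The exact width for x events in n is the 0.975 quantile of Beta(x+1, n−x) minus the 0.025 quantile of Beta(x, n−x+1), maximised over x.

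| n | Wald maximum | Exact maximum |
|---|---|---|
| 20 | 0.438 | 0.456 |
| 30 | 0.358 | 0.374 |
| 40 | 0.310 | 0.324 |
| 45 | 0.292 | 0.305 |

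At 40 the stated 0.309 is narrower than the exact maximum by 0.324 − 0.309 = 0.015. Going from 40 to 45 narrows the exact maximum by 0.324 − 0.305 = 0.019.

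**4. Illustration at low DLT counts.** Section 4.1 reports no DLTs in the phase I and II studies, so small counts are plausible. With zero events the two-sided exact upper limit is 1 − 0.025^(1/n). With one event it is the 0.975 quantile of Beta(2, n−1).

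| n | Upper limit, 0 DLTs | Upper limit, 1 DLT |
|---|---|---|
| 30 | 11.6% | 17.2% |
| 40 | 8.8% | 13.2% |
| 45 | 7.9% | 11.8% |

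These limits show what the choice of size does to the reported interval. The plan sets no criterion that uses them.

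**The case against.** The strongest reply is that the statements can mostly be read together. Twenty is the size if the trial halts. Forty-five is the top of every stated range and was introduced as an expansion, so it is a ceiling. The 30 to 45 in 3.2 is worded as a forecast, and the step in 4.1 is mandatory once the interim is passed. On that reading the sizes do not all conflict, and nothing instructs anyone to stop at 30.

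Much of this stands. It narrows the conflict to two places: the lower end (30 against 20) and the completed cohort (40 against up to 45). It does not remove them. If 20 means halted, the 30 has no source in the accrual rule, and no instruction says how accrual passes 40.

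A reader might also infer that the primary safety conclusion is judged against 10%, so that a cohort of 30 could not succeed even with zero DLTs. The documents do not support this. Section 4.1 uses 10% only as a halting threshold, applied to the lower confidence bound, and neither 4.1 nor 4.2 aims to exclude 10% from above. The contrast between 30 and 40 is also fragile. With one DLT the upper limit exceeds 10% at 30, 40 and 45 alike, and with a one-sided 95% limit zero DLTs in 30 gives 1 − 0.05^(1/30) = 9.5%.

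Nor does the text support an inference that the open range lets accrual end when the DLT count looks good. The only planned look is at 20, and it can only halt the trial for excess toxicity.

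**Conclusion.** The inconsistency is real in the current text and should be corrected. The accrual rule ends at 20 or 40, the stated ranges start at 20 or 30 and end at 45, and no precision is given for 30 or 45. The planned ceiling is 5 naive patients above what the rule delivers (45 against 40, or 62 against 57 in total).

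In precision terms the effect is modest: an exact maximum width of 0.374 at 30, 0.324 at 40 and 0.305 at 45. The stated 0.309 is a Wald value for 40, and it understates the exact maximum there by about 0.015. These figures assume the two-sided exact 95% interval, which the plan's own 11.89% confirms.

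The halting rule at 20 and the planned exact-interval analysis are unaffected. The conclusion rests on the conflicting sizes alone and does not depend on any test against 10%.

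**What to change.** State one accrual rule, in the same terms, in 1.0, 3.2 and 4.1: 20 vaccine-naive patients if the trial is halted at the interim, otherwise at least 40 and up to 45.

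- In 4.1, change the post-interim step from 20 further patients to 20 to 25, which brings the rule into line with the expansion sentence.
- Remove the lower end of 30 from 1.0 and 3.2. Show 20 only as the halted size.
- Replace the Wald widths with exact ones: 0.456 at 20, 0.324 at 40 and 0.305 at 45.

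The floor of 40 is what 4.1 already commits to. Making 45 mandatory would go further than the plan, which treats it as a ceiling.

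The cost is wording in three sections and recalculated widths, with no patients beyond the 45 already allowed. The downside is that the option to end accrual at 30, which 1.0 and 3.2 appear to leave open, is lost.
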